10.1.7. Data quality assurance

The Sponsor must keep coded data from clinical studies for a minimum of 30 years after the end of the study to ensure the validity of the research. This will also be the case if a participant stopped study participation prematurely. The Sponsor will also keep coded data, where needed because of legal action or an investigation involving the Sponsor.

The Investigator should maintain a record of the location(s) of their respective essential documents, including source documents (see [Glossary of terms](#) for the exact definition of essential and source documents). The document storage system used during the trial and for archiving (irrespective of the type of media used) should provide for document identification, version history, search, and retrieval.

Essential trial documents may be added or removed where justified (in advance of trial initiation) based on their importance and relevance to the trial. When a copy is used to replace an original document (e.g., source documents, case report form), the copy should fulfil the requirements for certified copies (see [Glossary of terms](#) for the exact definition of certified copies).

All participant data related to the study will be recorded on printed or eCRF unless transmitted to the GSK/IQVIA electronically (e.g., laboratory data). The Investigator is responsible for verifying that data entries are accurate and correct by physically or electronically signing the eCRF.

The Investigator must maintain adequate and accurate source documents and trial records that include all pertinent observations on each of the site's trial participants (see [Glossary of terms](#) for the exact definition of source documents) that supports information entered in the eCRF.

The Investigator must permit study-related monitoring, audits, IRB/IEC review, and regulatory agency inspections and provide direct access to source documents or certified copies for such review and inspection.

IQVIA is responsible for the data management of this study including quality checking of the source data (see [Glossary of terms](#) for the exact definition of source data).

Study monitors will perform ongoing source data verification to confirm that data entered in the eCRF by authorised site personnel are attributable, legible, contemporaneous, original, accurate, and complete. Changes to source data must be traceable, not obscure the original entry, and be fully explained if necessary (e.g., via an audit trail). The safety and rights of participants must be protected, and the study conducted in accordance with the currently approved protocol and any other study agreements, ICH GCP, and all applicable regulatory requirements.

Quality tolerance limits (QTLs) will be predefined in the Risk Management Plan Study Risk Register (GVGH Study Risk-Based Quality Assessment Template) to identify systematic issues that can impact participant safety and/or the reliability of study results. These predefined parameters will be monitored during the study. Important deviations from the QTLs and remedial actions taken will be summarised in the clinical study report (CSR).

Trial records and source documents pertaining to the conduct of this study, including signed ICFs, must be retained by the Investigator for 25 years from issuance of the final CSR/equivalent summary unless local regulations or institutional policies require a longer retention period. No records may be destroyed during the retention period without the written approval of the Sponsor. No records may be transferred to another location or party without written notification to the Sponsor.

10.1.8. Source documents

Source documents provide evidence to establish the existence of the participant and substantiate the integrity of collected data. The Investigator should maintain a record of the location(s) of their source documents.

Data transcribed into the eCRF from source documents must be consistent with those source documents; any discrepancies must be explained. The Investigator may need to request previous medical records or transfer records, depending on the study. Also, current medical records must be available.

Definitions of what constitutes source data and documents can be found in the [Glossary of terms](#).

10.1.9. Study and site start and closure

First act of recruitment

The first act of recruitment, defined by either the date of first contact with a potential study participant or date of publication of an advertisement for this specific study (whichever is earlier), will signify the official start of the study.

Study/Site termination

GSK or its designee reserves the right to close the study site or terminate the study at any time for any reason at its sole discretion, provided there is sufficient notice given to account for all participants safe exit from study.

Regular closure of study sites will occur upon study completion. A study site is considered closed when all required data/documents and study supplies have been collected and a study site closure visit has been performed.

The Investigator may initiate study site closure at any time, provided there is reasonable cause and enough notice in advance of the intended termination.

Reasons for the early closure of a study site by the Sponsor or Investigator may include but are not limited to:

- Failure of the Investigator to comply with the protocol, the requirements of the IRB/IEC or local health authorities, the Sponsor's procedures, or GCP guidelines
- Inadequate recruitment of participants by the Investigator
- Discontinuation of further study intervention development
- Total number of participants included earlier than expected

If the study is prematurely terminated or suspended, GSK/IQVIA shall promptly inform the investigators, the IECs/IRBs, the regulatory authorities, and any contract research organisation(s) used in the study of the reason for termination or suspension, as specified by the applicable regulatory requirements. The Investigator shall promptly inform the participant and should assure appropriate participant therapy and/or follow-up.

At the end of the study, the Investigator will:

- Review data collected to ensure accuracy and completeness
- Complete the Study Conclusion screen in the eCRF.

10.1.10. Publication policy

GSK aims to submit the results of the study for publication in searchable, peer reviewed scientific literature within 18 months from the Last Subject Last Visit (safety phone contact, Day 337) for interventional studies and follows the guidance from the International Committee of Medical Journal Editors.

10.2. Appendix 2: Clinical laboratory tests (Amended, 21 August 2023)

Anti-Vi antigen IgG determination from serum

Anti-Vi specific IgG antibodies will be measured by a *qualified, fit for purpose (Amended 21 August 2023)*, anti-Vi IgG ELISA *assay*. The assay *setup, qualification, and serology testing* will be performed in a laboratory designated by GVGH.

Anti-O antigen IgG determination from serum

Anti-O:2 IgG antibodies in serum will be measured by an ELISA assay, which uses a standard curve with an assigned value of ELISA units/mL. This assay, developed by GVGH, is based on a method previously reported [Launay, 2017] and will be performed in a laboratory designated by GVGH. The ELISA is performed using *S. Paratyphi A O* antigen as coating antigen. For this assay, a standard curve is run in duplicate on each plate. Results are expressed in ELISA units (EU)/mL of serum. One unit equals the reciprocal of the dilution to give an optical density of 1.

CCI

10.2.1. Protocol-required safety laboratory assessments

Table 17 shows the protocol-required safety assays, which will be performed by the local laboratory.

Table 17 Protocol-required safety laboratory assessments

Laboratory assessments	Parameters
Safety Screening laboratory assays	
Haematology	
 • Leukocytes (white blood cells [WBC]) • Erythrocytes (red blood cells [RBC]) • Haemoglobin • Haematocrit • Platelets • Eosinophils • Basophils • Neutrophils • Monocytes • Lymphocytes
Clinical chemistry	
 • Total bilirubin • Aspartic aminotransferase (AST) • Alanine aminotransferase (ALT) • γ-Glutamyl transferase (γ-GT) • Lactic dehydrogenase (LDH) • Alkaline phosphatase (AP) • Total proteins • Glucose (random glucose) • Blood urea (BU)* • Creatinine • Sodium • Potassium
Other Screening tests	
 • Hepatitis B surface antigen antibodies • Hepatitis C virus antibodies • HIV antibodies • Prothrombin time • Blood human chorionic gonadotropin (hCG) pregnancy test (for women of childbearing potential)
Pre/Post-vaccination safety laboratory assays (Visit 1, Visit 2, Visit 4, and Visit 5)	
Haematology	
 • Leukocytes (WBC) • Erythrocytes (RBC) • Haemoglobin • Haematocrit • Platelets • Eosinophils • Basophils • Neutrophils • Monocytes • Lymphocytes
Clinical chemistry	
 • Creatinine • AST • ALT • BU*
Other tests	
 • Urine hCG pregnancy test (as needed for women of childbearing potential; required at Visit 1 and Visit 4)

*BU will be converted to blood urea nitrogen for grading purposes. Refer to Section 10.9.

ALT=alanine aminotransferase; AST=aspartate aminotransferase; BU=blood urea; hCG=human chorionic gonadotropin; RBC=red blood cell; SAE=serious adverse event; ULN=upper limit of normal; WBC=white blood cell
NOTES:

All haematology assay outputs should be reported in absolute values.

All events of ALT $\geq 3 \times$ upper limit of normal (ULN) and bilirubin $\geq 2 \times$ ULN ($>35\%$ direct bilirubin) or ALT $\geq 3 \times$ ULN, which may indicate severe liver injury (possible Hy's Law), must be reported as an SAE.

10.3. Appendix 3: Adverse Events: definitions and procedures for recording, evaluating, follow-up, and reporting Definition of AE

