1.2. Schema

1.3. Schedule of Activities (SoA)

Table 1 Schedule of Activities (SoA)

Type of contact	Screening period	Visit 1 (Priming Vacc)	Sentinel participant safety phone contact	Reminder phone contact 1	Visit 2	Visit 3	Visit 4 (Booster Vacc)	Reminder phone contact 2	Visit 5	Visit 6	Follow-up safety phone contact
Time points	Day -21 to Day -1	Day 1	Day 2	Day 4	Day 8	Day 29	Day 169	Day 172	Day 176	Day 197	Day 337
Informed consent (Section 10.1.3)	•										
Check of inclusion/exclusion criteria (Sections 5.1 and 5.2)	•	•					•				
Collection of demographic data (Section 8.2.1.1)	•										
Medical history (Section 8.2.1.2)	•										
Physical examination (including vital sign assessment and body temperature measurement) (Section 8.2.1.3)	•	•					•				
Symptom-directed physical examination (Section 8.2.1.3)					○	○			○	○	
Height and weight measurement (Section 8.2.1.3)	•										
Randomisation (Section 6.3)		•									
Study intervention											
Check of contraindications and warnings, and precautions to vaccination (Sections 7.1.1 and 8.2.1.6)	○	○					○				
Check of criteria for temporary delay for enrolment and/or study intervention administration (Section 5.5)	○	○					○				

CONFIDENTIAL

205480 (TYPH-PARATYPH A CONJ VI-CRM O2-CRM GVGH-001 (H02_01TP))
 Protocol Amendment 2 Final

Type of contact	Screening period	Visit 1 (Priming Vacc)	Sentinel participant safety phone contact	Reminder phone contact 1	Visit 2	Visit 3	Visit 4 (Booster Vacc)	Reminder phone contact 2	Visit 5	Visit 6	Follow-up safety phone contact
Time points	Day -21 to Day -1	Day 1	Day 2	Day 4	Day 8	Day 29	Day 169	Day 172	Day 176	Day 197	Day 337
Pregnancy test (Section 8.2.1.4)	● ¹	● ²					● ²				
Study intervention allocation (Section 6.3)		●									
Administration of the Vi-CRM197+O:2-CRM ₁₉₇ vaccine (low or full dose, with or without Alum), or control		● ³					● ⁴				
Laboratory assessments											
Blood sampling for antibody determination (~10 mL)		● ⁵				●	● ⁵		●	●	
Blood collection for assay standard generation (~15 mL)										●	
Blood sampling for safety Screening laboratory assays (refer to Table 17) (~20 mL)	●										
Blood sampling for safety laboratory assays (haematological and clinical chemistry analyses) (~13.5 mL)		● ^{5,6}			●		● ⁵		●		
Safety assessments											
Recording of any concomitant medication/vaccination (Section 6.8)	●	●	● ⁷		●	●	●		●	●	
Recording of any intercurrent medical conditions (Section 9.3.1)		●	● ⁷		●	●	●		●	●	

CONFIDENTIAL

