5. STUDY POPULATION

Adherence to the inclusion and exclusion criteria specified in the protocol is essential. Deviations from these criteria are not allowed because they can jeopardise the scientific integrity, regulatory acceptability of the study or safety of the participant.

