5.1. Inclusion criteria

All participants must satisfy ALL the following criteria at study entry:

- Participants who, in the opinion of the Investigator, can and will comply with the requirements of the Protocol (e.g., completion of the diary cards, return for follow-up visits).
- Written informed consent obtained from the participant prior to performance of any study specific procedure.
- Healthy participants as established by medical history, clinical examination, and Screening laboratory investigations.
- Participant satisfying Screening requirements.
- Participant seronegative for human immunodeficiency virus, hepatitis B, and hepatitis C at Screening.

- A male or female participant between, and including, 18 and 50 years of age at the time of the first study intervention administration.
- Female participants of non-childbearing potential may be enrolled in the study. Non-childbearing potential is defined as pre-menarche, current bilateral tubal ligation or occlusion, hysterectomy, bilateral ovariectomy or post-menopause. Refer to Section 10.4.1 for definitions of women of childbearing potential, menarche, and menopause.
- Female participants of childbearing potential may be enrolled in the study if the participant:
 - has practiced adequate contraception for 1 month prior to study intervention administration, and
 - has a negative pregnancy test on the day of study intervention administration, and
 - has agreed to continue adequate contraception during the entire treatment period and for 1 month after completion of the study intervention administration series.

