5.2.1. Medical conditions

- Progressive, unstable, or uncontrolled clinical conditions.
- History of any reaction or hypersensitivity likely to be exacerbated by any component of the vaccine.
- Hypersensitivity, including allergy, to medicinal products or medical equipment whose use is foreseen in this study.
- Clinical conditions representing a contraindication to intramuscular vaccination and blood draws.
- Any confirmed or suspected immunosuppressive or immunodeficient condition, based on medical history and physical examination (no laboratory testing required).
- Any behavioural or cognitive impairment or psychiatric disease that, in the opinion of the Investigator, may interfere with the participant's ability to participate in the study.
- Acute* or chronic illness, clinically significant pulmonary, cardiovascular, hepatic, or renal functional abnormality, as determined by physical examination or laboratory screening tests.

*Participants with a minor illness (such as mild diarrhoea or mild upper respiratory infection) without fever may be enrolled at the discretion of the Investigator.

- Any clinically significant* haematological (haemoglobin level, white blood cell, lymphocyte, neutrophil, eosinophil, platelet, red blood cell count and erythrocyte mean corpuscular volume) and/or biochemical (alanine aminotransferase [ALT], aspartate aminotransferase [AST], creatinine, and total protein) laboratory abnormality.
- *The Investigator should use his/her clinical judgement to decide which abnormalities are clinically significant.
- Confirmed positive COVID-19 test during the period starting 14 days before the first administration of study vaccines (Day -14 to Day 1).
- Any other clinical condition that, in the opinion of the Investigator, might pose additional risk to the participant due to participation in the study.
- Confirmed or suspected autoimmune diseases (e.g., vitiligo, autoimmune thyroiditis).

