5.2.2. Prior/Concomitant therapy

- Previous administration of any type of Typhoid vaccine (Ty21a, Vi-PS, or Typhoid conjugate vaccine).
- Use of any investigational or non-registered product (drug, vaccine, or medical device) other than the study interventions during the period starting 30 days before the first administration of study vaccines (Day -30 to Day 1), or planned use during the study period.
- A vaccine not foreseen by the study protocol administered during the period starting at -14 days before the first dose (-21 days in the case of live vaccines) and ending 28 days after the last dose of study intervention administration*, with the exception of flu and COVID-19 vaccines, administered during the period starting at 7 days before and 7 days after each dose (14 days before and 14 days after in case of live vaccines).

*In case emergency mass vaccination for an unforeseen public health threat (e.g., a pandemic) is recommended and/or organised by public health authorities outside the routine authorisation programme, the time period described above can be reduced if, necessary for that vaccine, provided it is used according to the local governmental recommendations and that the Sponsor is notified accordingly. When regulations allow, the recommended time intervals for administration of these vaccines are at least 7 days before or 7 days after (at least 14 days before or 14 days after in case of live vaccines) each dose of study intervention administration.

- Administration of long-acting immune-modifying drugs at any time during the study period (e.g., infliximab).
- Administration of immunoglobulins and/or any blood products or plasma derivatives during the period starting 3 months before the administration of the first dose of study intervention or planned administration during the study period.

- Chronic administration (defined as more than 14 days in total) of immunosuppressants or other immune-modifying drugs during the period starting 3 months prior to the first study intervention dose. For corticosteroids, this will mean prednisone equivalent ≥ 20 mg/day for adult participants. Inhaled and topical steroids are allowed.

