10. DEMOGRAPHIC AND OTHER BASELINE CHARACTERISTICS

Individual participant demographics and baseline characteristics (medical history and results from viral serology, and urine pregnancy tests) will be presented in listings.

Demographic characteristics such as age, sex, race, height, weight, and body mass index (BMI) will be

Document: \\dccar2dnetvnasc01p-lan1.quintiles.net\cp_ops\PROJECTS\Glaxo SmithKline\GSK205480_HAB61752\SAP
Author: PPD Version Number: 1.0
Version Date: 25OCT2022

Template No: CS_TP_BS016 – Revision 7
Effective Date: 01Nov2021

Reference: CS_WI_BS005

summarized and tabulated for each treatment, each step and for all participants overall. Descriptive statistics (mean, median and standard deviation) will be presented for age, height, weight, and BMI. Frequency counts and percentages will be presented for sex, race, and step.

No statistical testing will be carried out for demographic or other baseline characteristics.

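### The only hepatitis B test in the screening panel (Protocol Table 17) is for antibodies to the surface antigen, which does not fit the Section 5.1 requirement to be seronegative for hepatitis B

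*Protocol*

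**What the plan says.** Protocol Section 5.1 makes this an entry criterion: "Participant seronegative for human immunodeficiency virus, hepatitis B, and hepatitis C at Screening". It does not say which hepatitis B marker is meant.

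The Schedule of Activities (Section 1.3) defines the screening blood draw by pointing to Table 17. Section 10.2.1 introduces that table in these words: "Table 17 shows the protocol-required safety assays, which will be performed by the local laboratory". Under the other screening tests, Table 17 has one hepatitis B entry, "Hepatitis B surface antigen antibodies", beside antibody tests for hepatitis C virus and HIV. No test for the surface antigen itself, and no other hepatitis B marker, appears in the Protocol or the SAP.

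Three further passages bear on the reading:

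- Section 5, on the entry criteria: "Deviations from these criteria are not allowed because they can jeopardise the scientific integrity".
- Section 5.2.2 bars any previous typhoid vaccine. Other vaccines are barred only within a limited window: "A vaccine not foreseen by the study protocol administered during the period starting at -14 days before the first dose", with an end point after the last dose. A past hepatitis B vaccination is not an exclusion.
- SAP Section 10 covers screening serology only as a listing of "results from viral serology, and urine pregnancy tests", with no marker and no definition of a negative result.

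**The concern.** For HIV and hepatitis C, an antibody test suits a requirement to be seronegative. For hepatitis B it does not, because the antibody named in Table 17 marks vaccination or resolved infection rather than current infection. Used as the eligibility test, it works against the evident purpose of the criterion. It turns away healthy vaccinated adults and does not itself detect people who carry the virus.

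This is a first-in-human trial in healthy adults. ALT and AST at Day 8 and Day 176 enter the primary laboratory endpoint (Sections 9.4.1 and 10.2.1) and count toward holding rule 2c (Section 8.2.2.3, Table 11). An unrecognised hepatitis B infection is a competing explanation for a raised liver enzyme, and the reviewing committee would want to know of it.

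The site is also left without a clean course. If it enrols vaccinated adults despite a positive result on the listed test, they breach Section 5.1 as written, and SAP Section 11.2 names eligibility violations among the deviations that lead to elimination from the per-protocol set. If it runs the antigen test instead, it omits an assay that the protocol requires.

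**Working it through.** No sample size, rate or error probability is involved, and the plan states no figure to reproduce. The check sets the passages side by side.

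**Step 1. What seronegative means on the listed test.** Section 5.1 names no marker, the Schedule of Activities sends the screening draw to Table 17, and Table 17 has one hepatitis B entry. Read literally, seronegative for hepatitis B means negative for antibodies to the surface antigen.

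**Step 2. Apply that reading to each kind of screenee.** The second column is general immunology; the third follows from Section 5.1.

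| Screenee | Listed test | Hepatitis B part of Section 5.1 |
|---|---|---|
| Never vaccinated, never infected | negative | passes |
| Successfully vaccinated | positive | fails |
| Resolved infection with antibody | positive | fails |
| Surface-antigen-positive carrier without antibody | negative | passes |

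The second and fourth rows are the problem. The second conflicts with Section 5.2.2, which does not exclude hepatitis B vaccinees. The fourth leaves the infection undetected by the test meant to find it.

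**Step 3. Check what else could stop a carrier.** Section 5.1 requires good health by history, examination and screening laboratory tests. Section 5.2.1 excludes "Acute* or chronic illness, clinically significant pulmonary, cardiovascular, hepatic, or renal functional abnormality, as determined by physical examination or laboratory screening tests", and separately any clinically significant ALT or AST abnormality. The Table 17 screening panel includes bilirubin, AST, ALT, γ-GT, alkaline phosphatase and prothrombin time. Carriers with a known diagnosis, or with clinically significant liver abnormality, have several routes to exclusion. The remaining gap is the undiagnosed carrier with no such abnormality.

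**Step 4. Link to the holding rule.**

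- Rule 2c includes any Grade 3 or higher abnormality in the pre-specified laboratory parameters at 7 days after vaccination. That part of the rule has no causality condition.
- For ALT and AST, Grade 3 starts above 5.0 times the upper limit of normal (Section 10.9).
- The threshold is at least 1 participant in Step 1a or 1b, and at least 2 in Step 2.
- Table 11 sets thresholds by Step, not by arm. The participants at risk of triggering the rule in Step 1a or 1b are therefore 12 active + 6 control = 18.

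**Step 5. Size.** The documents give no hepatitis B vaccination, antibody or carriage rate for the screened population, so the number wrongly excluded or wrongly admitted cannot be calculated.

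**The case against.** The strongest reply is that this is a wording slip with no operational effect. Section 8.1.5 says the safety laboratory assessments follow the clinical laboratory manual, which is not among the documents, and the local laboratory may run the antigen test as routine. That is plausible, and it lowers the severity. It does not remove the defect, because the protocol is the document that sets eligibility and nothing in it or in the SAP corrects the entry.

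It can also be said that seronegative and antibodies agree as words, so the two passages do not formally contradict each other. That is correct. The fault is the wrong marker for the evident purpose, and seeing it takes standard immunology that the documents do not state.

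Three stronger readings are tempting, and the documents do not support them:

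- A reader might infer that people with active viral liver disease would be enrolled. The checks in Step 3 give several routes to exclude them; the gap is narrower.
- A reader might infer that a hepatitis flare would halt the trial and be taken for a vaccine effect. That needs a carrier to be enrolled and then to reach Grade 3 at the 7-day sample, and no probability is given for either. Rule 2c pauses dosing for review. An ad hoc safety committee meeting follows (Section 8.2.2.2), that committee works from unblinded data (Section 8.2.2), and a stop-or-restart decision is then taken (Section 8.2.2.3).
- A reader might put a number on recruitment. If, say, 30% to 80% of otherwise eligible screenees were antibody-positive, filling 96 places would take about 96/(1 − 0.30) = 137 to 96/(1 − 0.80) = 480 of them. Those percentages are an assumption with no basis in the documents, and the result only restates it.

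Selection for being unvaccinated would also act before randomisation and apply to every arm within a Step (Section 6.3.2). No bias in a between-group comparison is shown.

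**Conclusion.** The point holds as a wrong eligibility marker in the text. Table 17 and Section 5.1, taken together with the ban on deviations, fail a healthy hepatitis B-vaccinated adult whom Section 5.2.2 does not exclude. They could also admit an undiagnosed surface-antigen-positive carrier with no clinically significant liver abnormality. The conclusion rests on two assumptions: that the text is applied literally, and the general immunology that vaccination produces the listed antibody and carriers typically lack it.

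The size is unknown. What can be said is that a single Grade 3 ALT or AST value in such a participant would by itself meet rule 2c in Step 1a or 1b, counted among all 18 participants of that Step. Because the entry is probably a slip and other checks cover part of the gap, this is a should-fix correction. It is not evidence that carriers were enrolled or that any estimate is biased.

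**What to change.** Reconcile the hepatitis B entry in Table 17 with the hepatitis B part of the Section 5.1 criterion so that both name the same marker of current infection. The entry reads as a slip for the surface antigen test. State what result counts as negative. Confirm that the laboratory manual and the assay actually run agree with the corrected text. The hepatitis C and HIV entries need no change.

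The cost is one line in Table 17, one in Section 5.1, and a query to the local laboratory. The antigen test is an equivalent routine assay and should need no extra blood. If the antigen test has been used throughout, this only brings the protocol into line with practice. If the antibody test has been used, the sponsor should review the screening log and the serology listing for people failed or admitted on that result.
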